CLINICAL TRIAL PROTOCOL

		Document Number:	c03122592-02
BI Trial No.:	1245.107		
BI Investigational Product:	Jardiance®, Empagliflozin		
Title:	A 52-week randomised, double-blind, placebo-controlled, parallel-group, efficacy and safety study of empagliflozin once daily, as add-on to insulin in Japanese patients with Type 2 Diabetes Mellitus with insufficient glycaemic control		
Brief Title:	Empa add-on to Insulin (Japan)		
Clinical Phase:	IV		
Trial Clinical Monitor:	Phone: _____ Fax: _____		
Coordinating Investigator:	Phone/Fax: _____		
Status:	Final Protocol		
Version and Date:	Version:	Date:	
	2.0	13 September 2016	
Page 1 of 72			
Proprietary confidential information. © 2016 Boehringer Ingelheim International GmbH or one or more of its affiliated companies. All rights reserved. This document may not - in full or in part - be passed on, reproduced, published or otherwise used without prior written permission.			

CLINICAL TRIAL PROTOCOL SYNOPSIS

Name of company:	Boehringer Ingelheim	
Name of finished product:	Jardiance®	
Name of active ingredient:	Empagliflozin	
Protocol date: 1 SEP 2015	Trial number: 1245.107	Revision date: 13 SEP 2016
Title of trial:	A 52-week randomised, double-blind, placebo-controlled, parallel-group, efficacy and safety study of empagliflozin once daily, as add-on to insulin in Japanese patients with Type 2 Diabetes Mellitus with insufficient glycaemic control	
Coordinating Investigator:		
Trial site:	Multi-centre trial in Japan	
Clinical phase:	IV	
Objective:	The objective of the study is to investigate the efficacy and safety of empagliflozin (10 mg and 25 mg, once daily) compared to placebo given for 16 weeks as add-on therapy to stable insulin treatment and the long-term safety and efficacy of empagliflozin (10 mg and 25 mg, once daily) compared to placebo given for an additional 36 weeks as add-on therapy to adjustable-dose insulin treatment in Japanese patients with type 2 diabetes mellitus (T2DM) with insufficient glycaemic control	
Methodology:	Randomised, double-blind, placebo-controlled, parallel group	
No. of patients:		
total entered:	267 patients (399 patients enrolled)	
each treatment:	3 treatment groups, 1:1:1 ratio of randomisation Empagliflozin 10 mg : 89 patients Empagliflozin 25 mg : 89 patients Placebo : 89 patients	
Diagnosis :	Type 2 Diabetes Mellitus	

Proprietary confidential information © 2016 Boehringer Ingelheim International GmbH or one or more of its affiliated companies

Name of company:	Boehringer Ingelheim	
Name of finished product:	Jardiance®	
Name of active ingredient:	Empagliflozin	
Protocol date: 1 SEP 2015	Trial number: 1245.107	Revision date: 13 SEP 2016
Main criteria for inclusion:	
1. Diagnosis of type 2 diabetes mellitus prior to informed consent. This diagnosis should be confirmed by clinical judgment and negative results of Anti-GAD antibody and Anti-IA-2 antibody at Visit 1 (screening).2. Male and female patients on diet and exercise regimen who are pre-treated with any insulin therapy^{a)} alone^{c)} or in combination with 1 oral antidiabetic drug (OAD)^{b), c)} for at least 12 weeks prior to Visit 1 (screening).
a) Any kind of insulin therapy (Basal-Bolus therapy, Bolus insulin therapy, Premix insulin therapy and Basal insulin therapy) approved in Japan is allowed. The choices of insulin product, dosage and usage have to follow respective insulin product label in Japan at Visit 1 (screening).b) Sulfonylurea is permitted as a pre-treatment drug only if the dose is not more than a half of daily maximum approved dose. Any other OADs except thiazolidinedione and SGLT-2 inhibitors are allowed at any dose within approved dose.c) If patients are pre-treated by insulin with 1 OAD at Visit 1, the OAD should be stopped and washed-out for 10 weeks prior to Visit 4 (placebo run-in). For patients receiving insulin alone at Visit 1, no wash-out (of any drug) is necessary. 
Insulin product and its usage must be unchanged at least from 12 weeks prior to Visit 1 (screening). Total prescribed insulin dose must be ≥ 10 U/day, and it has to be within a defined area at least 12 weeks prior to Visit 5 (randomization) in patients who are pre-treated by insulin alone and from Visit 1 in patients who are pre-treated by insulin in combination with 1 OAD.
 
The defined area is as follows,
 
In case of the insulin dose at 12 weeks prior to Visit 5 in patients who are pre-treated with insulin therapy alone (at Visit 1 in patients who are pre-treated with insulin in combination with 1
	

Proprietary confidential information © 2016 Boehringer Ingelheim International GmbH or one or more of its affiliated companies

Name of company:	Boehringer Ingelheim	
Name of finished product:	Jardiance®	
Name of active ingredient:	Empagliflozin	
Protocol date: 1 SEP 2015	Trial number: 1245.107	Revision date: 13 SEP 2016
	
OAD) is
 
 • ≥ 20 U/day: Within $+\/- 10\%$ change from the dose at Visit 5 is allowed. • ≥ 10 U/day and <20 U/day: Within $+\/- 2$ U change from the dose at Visit 5 is allowed. (insulin dose <10 U is not allowed prior to and at Visit 5) 
3. Fasting C-peptide: >0.5 ng/mL at Visit 4 in patients who are pre-treated with insulin alone (at Visit 2 in patients who are pre-treated with insulin in combination with 1 OAD)
 
4. Patients who are treated with insulin alone:
 
HbA_{1c} at Visit 1: $\geq 7.5\%$ and $\leq 10.0\%$
 
5. Patients who are treated with insulin with 1 OAD:
 
HbA_{1c} at Visit 1: $\geq 7.0\%$ and $\leq 9.5\%$
 
HbA_{1c} at Visit 4: $\geq 7.5\%$ and $\leq 10.0\%$
 
6. Age at informed consent: ≥ 20 years and <75
 
7. BMI (body mass index) at Visit 1 : >22 and ≤ 40 kg/m²
 
8. Signed and dated written informed consent by date of Visit 1 in accordance with GCP and Japanese legislation
	
Test product:	Empagliflozin	
dose:	10 mg and 25 mg	
mode of administration:	Oral administration	
Comparator products:	Placebo matching for empagliflozin	
dose:	Not applicable	
mode of administration:	Oral administration	

Proprietary confidential information © 2016 Boehringer Ingelheim International GmbH or one or more of its affiliated companies

Name of company:	Boehringer Ingelheim	
Name of finished product:	Jardiance®	
Name of active ingredient:	Empagliflozin	
Protocol date: 1 SEP 2015	Trial number: 1245.107	Revision date: 13 SEP 2016
Duration of treatment:	
Screening period: 1 week
 
Wash-out period (only for patients who are pre-treated by insulin with 1 OAD): 10 weeks
 
Placebo run-in period (open label): 2 weeks
 
Double-blind treatment period: 52 weeks
 
Follow-up period: 1 week
	
Endpoints	
Primary endpoint is the change from baseline in HbA_{1c} after 16 weeks of treatment.
 
The secondary endpoint is proportion of patients with drug-related adverse events during 52 weeks of treatment.
	
Safety criteria:	Adverse events, serious adverse events, adverse events of special interest, adverse events leading to discontinuation, hypoglycaemic adverse events, clinical laboratory assessments, vital signs	
Statistical methods:	
The primary analysis is an analysis of covariance (ANCOVA) comparing the change from baseline in HbA_{1c} after 16 weeks of treatment. The statistical model includes treatment, renal function and type of insulin therapies as fixed effects, and baseline HbA_{1c} as a covariate.
 
The hierarchical testing procedure will be used to evaluate superiority of empagliflozin 10 mg against placebo followed by superiority of empagliflozin 25mg against placebo, while maintaining the overall probability of type I error at 0.05 (two-sided).
 
Descriptive statistics will be used to analyse the safety endpoints.
	

Proprietary confidential information © 2016 Boehringer Ingelheim International GmbH or one or more of its affiliated companies

FLOW CHART

Trial period	Screening	Wash-out ¹		Placebo run-in	Double-blind treatment period 1 (fixed dose of insulin)							Double-blind treatment period 2 (adjustment of insulin dose permitted)							Follow up		
		5	5.1 ²		6	7	8	9	10	11	12	13	14	15	16	17	18	19/ EOT ¹²			
Visit	1	2 ¹	3	4 ¹														20/ F-up ¹⁴			
Study week	-3/-13	-12	-8	-2		1	2	4	8	12	16	20	24	28	32	36	40	44	48	EOT+1w	
Study day	-21/-91	-84	-56	-14	1	8	15	29	57	85	113	141	169	197	225	253	281	309	337	365	EOT+7
Visit window (in days)	+/-7	-7	+/-7	-7	na	+/-3	+/-3	+/-7	+/-7	+/-7	+/-7	+/-7	+/-7	+/-7	+/-7	+/-7	+/-7	+/-7	+/-7	+7	
Informed Consent	X																				
Medical history / concomitant diagnoses	X																				
Demographics	X																				
In-/Exclusion criteria	X			X	X ³																
Physical Examination					X						X							X	(X) ¹⁴		
Vital Signs ⁴	X	X	X	X	X	X	X	X	X	X	X	X	X	X	X	X	X	X	(X) ¹⁴		
Height	X																				
Diet and exercise counselling ¹⁸	X	X	X	X	X	X	X	X	X	X	X	X	X	X	X	X	X	X			
Review Food log, completed for 3 days ¹⁸		X	X	X	X	X	X	X	X	X	X	X	X	X	X	X	X	X			
12-lead-ECG ^{4,5}	X				X			X		X		X		X		X		X			
Pregnancy testing ⁶	X				X			X		X		X		X		X		X			
Safety Labs ^{4, 7}	X ^{10,11}			X	X	X ¹⁶	X ¹⁶	X	X ¹⁶	X	X ¹⁶	X	X ¹⁶	X	X ¹⁶	X	X ¹⁶	X	(X) ¹⁴		
FFA and Ketone bodies				X	X			X	X		X		X		X		X	X			
Bone markers				X					X			X			X		X	X			

Trial Protocol

Proprietary confidential information © 2016 Boehringer Ingelheim International GmbH or one or more of its affiliated companies

Trial period	Screening	Wash-out ¹		Placebo run-in	Double-blind treatment period 1 (fixed dose of insulin)							Double-blind treatment period 2 (adjustment of insulin dose permitted)							Follow up			
		1	2 ¹		4 ¹	5	5.1 ²	6	7	8	9	10	11	12	13	14	15	16	17	18	19/ EOT ¹²	20/ F-up ¹⁴
Visit																						
Study week	-3/-13	-12	-8	-2		1	2	4	8	12	16	20	24	28	32	36	40	44	48	52	EOT+1w	
Study day	-21/-91	-84	-56	-14	1	8	15	29	57	85	113	141	169	197	225	253	281	309	337	365	EOT+7	
Visit window (in days)	+/-7	-7	+/-7	-7	na	+/-3	+/-3	+/-7	+/-7	+/-7	+/-7	+/-7	+/-7	+/-7	+/-7	+/-7	+/-7	+/-7	+/-7	+/-7	+/-7	
Antibodies (Anti-GAD, Anti-IA-2)	X ¹¹																					
Fasting C-peptide ¹⁷		X ¹⁷		X ¹⁷																		
HbA _{1c}	X ¹¹			X ¹³	X				X		X			X			X		X		X	
SMBG measurement and log ⁸		X	X	X	X	X	X	X	X	X	X	X	X	X	X	X	X	X	X	X	X	
Adverse events		X	X	X	X	X	X	X	X	X	X	X	X	X	X	X	X	X	X	X	X	
Concomitant therapy	X	X	X	X	X	X	X	X	X	X	X	X	X	X	X	X	X	X	X	X	X	
IRT transaction	X ³			X ³	X ³			X	X	X	X	X	X	X	X	X	X	X	X	X		
Dispense placebo run-in medication ⁹				X																		
Medication compliance check					X			X	X	X	X	X	X	X	X	X	X	X	X	X	X	
Randomisation (via IRT)					X ³																	
Dispense double-blind medication ⁹					X			X	X	X	X	X	X	X	X	X	X	X	X	X		

Proprietary confidential information © 2016 Boehringer Ingelheim International GmbH or one or more of its affiliated companies

1. Only patients who are pretreated by insulin with 1 OAD proceed to the wash-out period and are requested to refrain from taking their OAD during the wash-out period. Patients who are pretreated by insulin therapy alone skip the washout period and proceed to the placebo run-in period. In either case, the next visit (i.e., Visit 2 or Visit 4) should be made after receiving the result of the laboratory tests performed at Visit 1.
2. The investigator or designated site staff makes a call to patients to confirm patient's safety through checking patient's food log, SMBG results, adverse events and concomitant therapies.
3. Inclusion and exclusion criteria should be checked before making the IRT call/notification.
4. Vital signs and ECG must be measured prior to blood sampling.
5. In addition to the visits indicated, ECG should be recorded in case of respective cardiac symptoms (indicating rhythm disorders or cardiac ischaemia)
6. For female patients (local urine pregnancy test in women of child bearing potential)
7. Fasting blood samples for central lab testing except for urine dipstick, which is to be done locally; upon positive result at site for leukocyte esterase (for WBC) or nitrites a midstream urine sample for urine culture (central lab analysis) should be taken.
8. Self-Monitoring Blood Glucose (SMBG) device to be provided at Visit 2 to patients who need wash-out of an OAD or at Visit 4 to patients who do not need washout. Patients should be instructed to monitor fasting blood glucose at least once daily before breakfast (if possible, it is recommended to monitor fasting blood glucose in preprandial state and before bedtime) and at any time the patient is symptomatic related to hypoglycaemia or hyperglycaemia through the entire study period (i.e., after providing the SMBG device until the end of follow-up). In addition, in 3 consecutive days in the week before each scheduled visit, patients will be requested to monitor fasting blood glucose at preprandial state (i.e., before breakfast, lunch and dinner), before bedtime and at any time when the patient is symptomatic. Patients are requested to maintain a diary with daily recordings of glucose values measured by SMBG and of insulin dose through the entire study period.
9. At all the visits which are marked on the [flow chart](#), the respective kit number has to be allocated to the patient via IRT.
10. Only includes liver transaminases (i.e. AST and ALT), ALP, serum creatinine, TSH and urinalysis.
11. No need to be collected in fasted state.
12. In case of early discontinuation from treatment, the end of treatment (EOT) visit has to be performed within 7 days of the last dose of the study drugs. And the follow up (F-up) visit has to be performed after 7 days of the EOT (with +7 days allowance).
13. Patients who are pretreated with insulin alone skip the HbA_{1c} measurement at Visit 4.
14. For patients who completed the trial without any persisting adverse event at EOT, a follow-up visit can be performed as a phone visit (only information on SMBG log, adverse events, and concomitant therapies are to be obtained). For patients who completed the trial with persisting adverse event(s) at EOT and patients who early discontinued the 52 weeks treatment period, an EOT and a follow-up visit (at the follow up-visit, physical examination, vital signs, and safety lab and should be performed additionally) should be performed at clinic visits.
- 15.
16. Only blood sampling for haematology and urinalysis will be performed.
17. C-peptide will be measured at Visit 2 in patients who need wash-out of an OAD or Visit 4 in patients who do not need wash-out.

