Insulin deficiency might lead to ketoacidosis which could be life-threatening if not recognized and appropriately treated. All patients in this trial will be made aware of this risk and be instructed not to reduce their insulin dose below Investigator recommendations.

Furthermore, patients will be reminded of insulin dose adjustment during “sick days” and of the importance of keeping themselves hydrated. Investigators should also differentiate deteriorating ketosis/DKA from any mild to moderate increase of ketones expected from the mechanism of action of empagliflozin, especially in the fasted state (e.g., in the morning).

The overall frequency of volume depletion defined in the IB was similar between empagliflozin and placebo. However, the frequency of volume depletion events was increased in patients at the age of 75 years or over treated with empagliflozin compared to placebo. Based on the mode of action of SGLT-2 inhibitors, osmotic diuresis may lead to a modest decrease in blood pressure and dehydration. Therefore, careful monitoring of volume status and electrolytes (e.g. physical examination, blood pressure measurements, and laboratory tests including haematocrit) is recommended. Also, patients will be requested to drink plenty of fluids as a precautionary measure. Temporary interruption of treatment with empagliflozin should be considered until the fluid loss is corrected.

Patients will be carefully selected for the trial in line with the eligibility criteria, to ensure, in investigator's judgement, that patients have a good understanding of their disease and how to

manage it. They should also be selected in terms of their ability to be compliant with the demands of the trial.

Beneficial effects like body weight reduction and a moderate blood pressure lowering are expected based on Phase III studies of empagliflozin and publications of other SGLT-2 inhibitors.

As with all drugs, the potential for hypersensitivity and allergic reactions has to be taken into consideration when empagliflozin is administered. Other risks to the patients are the risks inherent to any treatment such as unexpected adverse clinical or laboratory events.

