3.3.2 Inclusion criteria

1. Diagnosis of type 2 diabetes mellitus prior to informed consent. This diagnosis should be confirmed by clinical judgment and negative results of Anti-GAD antibody and Anti-IA-2 antibody at Visit 1 (screening).
2. Male and female patients on diet and exercise regimen who are pre-treated with any insulin therapy^{a)} alone^{c)} or in combination with 1 oral antidiabetic drug (OAD)^{b), c)} for at least 12 weeks prior to Visit 1 (screening).
 - a) Any kind of insulin therapy (Basal-Bolus therapy, Bolus insulin therapy, Premix insulin therapy and Basal insulin therapy) approved in Japan is allowed. The choices of insulin product, dosage and usage have to follow respective insulin product label in Japan at Visit 1 (screening).
 - b) Sulfonylurea is permitted as a pre-treatment drug only if the dose is not more than a half of daily maximum approved dose. Any other OADs except thiazolidinedione and SGLT-2 inhibitors are allowed at any dose within approved dose.
 - c) If patients are pre-treated by insulin with 1 OAD at Visit 1, the OAD should be stopped and washed-out for 10 weeks prior to Visit 4 (placebo run-in). For patients receiving insulin alone at Visit 1, no wash-out (of any drug) is necessary.

Insulin product and its usage must be unchanged at least from 12 weeks prior to Visit 1 (screening). Total prescribed dose must be ≥ 10 U/day, and it has to be within a defined area at least 12 weeks prior to Visit 5 (randomization) in patients who are pre-treated by insulin alone and from Visit 1 in patients who are pre-treated by insulin in combination with 1 OAD.

The defined area is as follows,

In case of the insulin dose at 12 weeks prior to Visit 5 in patients who are pre-treated with insulin therapy alone (at Visit 1 in patients who are pre-treated with insulin in combination with 1 OAD) is

- ≥ 20 U/day: Within $+\/- 10\%$ change from the dose at Visit 5 is allowed.
- ≥ 10 U/day and < 20 U/day: Within $+\/- 2$ U change from the dose at Visit 5 is allowed. (insulin dose < 10 U is not allowed prior to and at Visit 5)

3. Fasting C-peptide: > 0.5 ng/mL at Visit 4 in patients who are pre-treated with insulin alone (at Visit 2 in patients who are pre-treated with insulin in combination with 1 OAD)
4. Patients who are treated with insulin alone:
 - HbA_{1c} at Visit 1: $\geq 7.5\%$ and $\leq 10.0\%$ (HbA_{1c} at Visit 4 is to be skipped)
5. Patients who are treated with insulin with 1 OAD:

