5.3.3 Safety laboratory parameters

All safety laboratory samples (except at Visit 1) will be collected after a full overnight fast (nothing to eat or drink except water for at least 10 hours) and before investigational drug is taken as described in the [flow chart](#) and [Section 6](#). The blood sample at Visit 1 (screening visit) can be taken with the patient in a fasted or non-fasted state.

All parameters that will be determined during the trial conduct are listed in [Tables 5.3.3: 1](#) and [5.3.3: 2](#). The analysis will be performed by a central laboratory. The respective reference range and details about sample handling and shipment will be provided in the ISF (Lab Manual).

Reduced lab panels are planned for the following visits (For details, see the [flow chart](#)):

- For the screening Visit 1, laboratory only includes liver transaminases (i.e., AST and ALT), alkaline phosphatase, serum creatinine, thyroid stimulation hormone (TSH) , anti-GAD antibody, Ant-IA-2 antibody, FPG, HbA_{1c} and urinalysis.
- C-peptide will be measured at Visit 2 in patients who need washout an OAD or Visit 4 in patients who do not need washout period.
- Free fatty acid (FFA) and Blood ketone bodies will be measured at selected visits. For the details, see the [flow chart](#).
- Bone markers; iPTH (intact parathyroid hormone), 25OH Vitamin D, NTx in urine: planned at Visits 5, 10 and EOT.
- Hematology and urinalysis will also be measured at Visit 6, 7, 9 11, 12, 14, 15, 17 and 18.

Table 5.3.3: 1

Safety laboratory parameters – whole blood, serum or plasma

Haematology

- Haematocrit
- Haemoglobin
 - Reticulocyte count (reflex test if Hb outside normal range)
- Red blood cells (RBC)/Erythrocytes
- White blood cell (WBC)/Leukocytes
- Platelet count/Thrombocytes
- Differential automatic (relative and absolute count):
Neutrophils, eosinophils, basophils, monocytes, lymphocytes

Clinical chemistry

- Albumin
- ALP
- γ -GT (gamma-glutamyl transferase)
- ALT (alanine aminotransaminase, SGPT)
- AST (aspartate aminotransaminase, SGOT)
- Bicarbonate
- Bilirubin total, fractionated if increased
- C-peptide
- Calcium
- Chloride
- Creatinine
- Creatinine kinase (CK)
- hs troponin T (reflex tests if CK is elevated)
- Lactate dehydrogenase (LDH)
- Lipase
- Magnesium
- Phosphate
- Potassium
- Protein total
- Sodium
- TSH (only at Visit 1)
- Urea (BUN)
- Uric acid
- Cholesterol (total)
- HDL cholesterol
- Calculated LDL cholesterol

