6.2 DETAILS OF TRIAL PROCEDURES AT SELECTED VISITS

6.2.1 Screening and run-in periods

Screening Period

The screening visit is the only visit in this study that does not need to be done in fasting.

No trial procedures should be done unless the patient has consented to taking part in the trial.

Once they have consented, the patient is considered to be enrolled in the trial and should then be recorded in the enrolment log, and screening will be started. The patient should be registered in the IRT as a screened patient at Visit 1.

ECG and BP should always be measured before any blood samples are taken. For details regarding the correct method for measuring BP, see [Appendix 10.1](#).

At the end of the screening visit, patients will be given a food intake log/booklet which is requested to be completed for three consecutive days in the week prior to the next visit. Details of any patient who is screened for the study but is found to be ineligible must be entered in an enrolment log and documented in the eCRF.

Patients who are treated with insulin alone and qualify at Visit 1 will undergo a 2-week placebo run-in period. And patients who are treated with insulin in combination with one OAD and qualify at Visit 1 will undergo a 10-week wash-out period.

Wash-out Period

Only the patients who are treated with insulin in combination with one OAD as the previous treatments will undergo this period. These patients will be requested to wash-out the OAD at Visit 2. Patients who are treated with insulin alone will skip this period.

From Visit 2, the patients should be fasting (no food or drinks, water only for at least 10 hours) prior to each visit. And at Visit 2, patients will be requested not to take OAD on the morning of a visit before attending the clinic.

The patients will be provided Self-Monitoring Blood Glucose (SMBG) equipment and supplies at Visit 2. Instruction on the proper use of the SMBG equipment will be provided by site staff. Please refer to [Section 5.3.5 \(Self-Monitoring blood Glucose\)](#) for the details of measurement frequency and the record.

If the SMBG test reveals an overnight fasted blood glucose of >270 mg/dL (15.0 mmol/L), the patient should contact the study site for a visit as soon as possible, on ideally the next day

See [Section 5.3.5](#).

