11. DESCRIPTION OF GLOBAL AMENDMENT(S)

Number of global amendment	1
Date of CTP revision	13 September 2016
EudraCT number	
BI Trial number	1245.107
BI Investigational Product	Jardiance [®] , Empagliflozin
Title of protocol	A 52-week randomised, double-blind, placebo-controlled, parallel-group, efficacy and safety study of empagliflozin once daily, as add-on to insulin in Japanese patients with Type 2 Diabetes Mellitus with insufficient glycaemic control
To be implemented only after approval of the IRB	
To be implemented immediately in order to eliminate hazard – IRB to be notified of change with request for approval	
Can be implemented without IRB approval as changes involve logistical or administrative aspects only	
Section to be changed	3.3.2 and synopsis (Change 1)
Description of change	Text in inclusion criteria 2 is reformulated to: Insulin product and its usage must be unchanged at least from 12 weeks prior to Visit 1 (screening). Total prescribed dose must be ≥ 10 U/day and ≥ 0.2 U/kg/day , and it has to be within a defined area at least 12 weeks prior to Visit 5 (randomization) in patients who are pre-treated by insulin alone and from Visit 1 in patients who are pre-treated by insulin in combination with 1 OAD.
Rationale for change	To carry out the study in common clinical setting in Japan, the criterion of the dose of insulin is updated. (It is estimated that there are many T2DM patients who are treated with insulin which doses are more than or equal to 10U/day but below 0.2U/kg/day in common clinical setting in Japan)
Section to be changed	3.3.2 and synopsis (Chang 2)
Description of change	Inclusion criteria 3 is reformulated to: Fasting C-peptide: $\geq 0.6 > 0.5$ ng/mL at Visit 4 in patients who are pre-treated with insulin alone (at

Proprietary confidential information © 2016 Boehringer Ingelheim International GmbH or one or more of its affiliated companies

		Visit 2 in patients who are pre-treated with insulin in combination with 1 OAD)
Rationale for change		The criterion was set up to remove the patients who are in insulin-dependent state. The treatment Guide for Diabetes 2014-2015 says that C-peptide ≤ 0.5 is insulin-dependent state. To match with the treatment guide, this is updated.
Section to be changed		5.3.6.1 (Chang 3)

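### In patients washed out of an oral drug, the C-peptide entry criterion is tested only as wash-out begins and is not repeated off drug, so the same limit is applied under different conditions in the two pre-treatment cohorts

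*Protocol*

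**What the plan says.** Three places in the protocol fix the timing, and they agree.

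- Flow chart, footnote 17: "C-peptide will be measured at Visit 2 in patients who need wash-out of an OAD". The footnote assigns the other cohort's sample to Visit 4.
- Section 3.3.2, criterion 3: the limit of more than 0.5 ng/mL applies at Visit 4 for insulin alone, and "at Visit 2 in patients who are pre-treated with insulin in combination with 1 OAD". The synopsis repeats this.
- Section 5.3.3: "C-peptide will be measured at Visit 2 in patients who need washout an OAD or Visit 4 in patients who do not need washout period".

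Section 6.2.1 places the start of wash-out at the same visit: "These patients will be requested to wash-out the OAD at Visit 2". The only instruction about the OAD before the sample is that "at Visit 2, patients will be requested not to take OAD on the morning of a visit before attending the clinic".

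Permitted OADs (Section 3.3.2, criterion 2) are sulfonylureas up to half the maximum approved daily dose, and any other class except thiazolidinediones and SGLT-2 inhibitors. Total insulin dose must stay within 10% or 2 U from Visit 1 in this cohort.

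The purpose of the criterion appears in the rationale in Section 11: "The criterion was set up to remove the patients who are in insulin-dependent state". For HbA1c, criterion 5 sets a range for the wash-out cohort at Visit 1 and again at Visit 4.

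**The concern.** Patients on insulin alone show their C-peptide in the state in which they enter the double-blind period. Wash-out patients show it at the end of OAD treatment, and are then randomised after ten weeks without the OAD plus a two-week run-in, with insulin held nearly constant. The protocol does not rely on the pre-wash-out HbA1c alone in this cohort. It does rely on the pre-wash-out C-peptide, and gives no reason for the difference.

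If the OAD was supporting insulin secretion at Visit 2, a patient could pass on drug and be at or below 0.5 ng/mL off drug. The criterion exists to keep such patients out, and Section 2.3 says why insulin reserve matters here: "Insulin deficiency might lead to ketoacidosis which could be life-threatening if not recognized and appropriately treated". What is at stake is patient safety and a consistent entry rule, not the treatment comparison.

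**Working it through.** **Timing (from the flow chart).** Visit 2 is day -84 and Visit 4 is day -14. The interval is -14 - (-84) = 70 days = 10.0 weeks, which reproduces the stated wash-out length. With the -7 day window at each visit it runs from 63 to 77 days. Randomisation is on day 1, so the C-peptide value is about 12 weeks old by then.

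**Conditions when each criterion is tested.**

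| Cohort | Test | Visit | State when tested |
|---|---|---|---|
| Insulin alone | C-peptide | 4 | Same regimen as at randomisation |
| Insulin + 1 OAD | C-peptide | 2 | One morning OAD dose withheld |
| Insulin + 1 OAD | HbA1c | 1 and 4 | On OAD, then 10 weeks off |

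**Effective limit (illustration).** Suppose an OAD raises fasting C-peptide by a fraction r. The documents give no value for r. A patient then passes on drug when the off-drug value exceeds 0.5/(1 + r):

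- r = 0: 0.500 ng/mL, so nobody is misclassified
- r = 10%: 0.5/1.10 = 0.455
- r = 25%: 0.5/1.25 = 0.400
- r = 50%: 0.5/1.50 = 0.333

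Patients between that value and 0.5 would pass at Visit 2 and be at or below the limit off drug.

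**Possible number of patients (assumptions throughout, except 178).** The 178 is 2 x 89 empagliflozin patients, from Section 7.7. Assume off-drug C-peptide in secretagogue users is log-normal with median 1.0 to 1.6 ng/mL and log-SD 0.5 to 0.7, and that r is 10% to 50%. With F the distribution function, the share of those passing at Visit 2 who are at or below the limit off drug is

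[F(0.5) - F(0.5/(1 + r))] / [1 - F(0.5/(1 + r))].

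- Lowest (r = 10%, median 1.6, log-SD 0.5): (0.0100 - 0.0059)/(1 - 0.0059) = 0.4%
- Centre (r = 25%, median 1.3, log-SD 0.6): (0.0556 - 0.0247)/(1 - 0.0247) = 3.2%
- Highest (r = 50%, median 1.0, log-SD 0.7): (0.1610 - 0.0583)/(1 - 0.0583) = 10.9%

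Assume further that 20% to 60% of patients come from the OAD cohort and that 40% to 70% of those used a secretagogue. Then 178 x 0.2 x 0.4 = 14 to 178 x 0.6 x 0.7 = 75 empagliflozin patients are concerned. The products run from 14 x 0.004 = 0.06 to 75 x 0.109 = 8.2 patients. At the midpoints, 178 x 0.40 x 0.55 = 39, and 39 x 0.032 is about 1.

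**The case against.** **The pharmacological step is not in the documents.** Nothing in the protocol or SAP says that any OAD raises C-peptide, or that such an effect is present at Visit 2 and gone by Visit 4. Section 3.2 justifies the wash-out by glycaemic control only. This stands. A reader might infer that insulin-dependent patients will pass in the wash-out cohort generally. The documents do not support that: several permitted classes need not act on insulin secretion, and at r = 0 no one is misclassified. The difference in test conditions, however, needs no pharmacology.

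**The text is consistent and may be deliberate.** Every place gives the same timing, and the 2016 amendment kept it. Testing early can identify ineligible patients before most of a ten-week wash-out. That is a reason to keep the Visit 2 test, but it does not argue against a second one.

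**Other screens apply.** These are negative anti-GAD and anti-IA-2 antibodies, exclusion for confirmed fasting glucose above 270 mg/dL in wash-out or run-in, the Visit 4 HbA1c ceiling of 10.0%, and the investigator's judgement of stability before randomisation (Section 6.2.2). They narrow the gap, and the counts above give no credit for them. None measures insulin reserve, and patients on insulin alone need a C-peptide result alongside their own antibody, glucose and HbA1c limits.

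**C-peptide may be in the Visit 4 panel anyway.** Table 5.3.3: 1 lists it under clinical chemistry without a visit limit. Footnote 17 and the bullet in Section 5.3.3 restrict it to one visit per cohort, and criterion 3 uses no later value.

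**Nothing happens to the inference.** Any misclassification occurs before randomisation, and the SAP (Table 6.2: 1, code A2.06) excludes no one from any analysis set for an out-of-range C-peptide. This stands in full.

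**Conclusion.** The asymmetry is documented. The wash-out cohort meets the 0.5 ng/mL limit at the start of wash-out and is not tested again off drug, while the insulin-alone cohort meets it in the state in which it is randomised.

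The consequence is conditional. It requires that a permitted secretagogue raises fasting C-peptide at Visit 2, and the documents give neither the direction nor the size of such an effect. It would concern secretagogue users only. Under the assumed ranges, about 0 to 8 of 178 empagliflozin patients (centre about 1) could be randomised at or below the limit. That range includes zero, and its top combines every unfavourable assumption. It shows scale and is not an estimate.

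A reader might go further and infer a biased treatment comparison or a loss of power. The documents give no basis for either. This is a cheap improvement to patient safety and to consistency between cohorts.

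**What to change.** Keep the Visit 2 test. In footnote 17, inclusion criterion 3 (with its synopsis copy) and Section 5.3.3, add a fasting C-peptide assay at Visit 4 for wash-out patients, and check it against the existing, unchanged criterion before randomisation at Visit 5, as is already done for insulin alone. If the sponsor prefers the present timing, the protocol should at least say why C-peptide, unlike HbA1c, is not re-tested after wash-out.

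The cost is a short amendment and one extra assay per wash-out patient, on fasting blood already drawn at Visit 4 for HbA1c and safety laboratory tests. No visit is added. The real downside is possibly a few run-in failures in patients who have already spent ten weeks off their OAD.
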